3.4. Data Collection

3.4.1. Discussion of VA research activities and data for non-VA research activities and non-VA data: All activities conducted under this study are for research purposes. The VABHCS is the coordinating center through which all recruitment, advertisements, participant assessments, and interventions associated with this research project will occur with the following exceptions. There will be a contract with the McLean Hospital for the acquisition, and analysis of the MRI data. There will be a contract with [name] for the analysis of the ECG data. The contracts and agreements will clearly state that the data acquired and analyzed are good and services and belong to the VA.

3.4.2. Data collection, storage, access, use, disclosure, and analysis:

3.4.2.1. Describe all data collection activities for VA research:

The collection of imaging data at the McLean Hospital was approved by VACO. There are three dependent variables: 1) Hamilton Depression Rating Scales, 2) Thalamic GABA levels, and 3) Respiratory Sinus Arrhythmia (RSA).

3.4.2.1. Psychological Scales: All data from screening and intervention assessments will take place at the VABHCS and will be put into REDCap. Evaluations at the McLean Hospital will be put into REDCap using a VA issued laptop.

3.4.2.2. Spectroscopic Data: All magnetic resonance imaging (MRI) and magnetic resonance spectroscopy (MRS) data used for analysis of GABA levels will be collected and analyzed at the McLean Hospital under a contract that will state that the data collected under the contract belongs to the VABHCS. The analyzed data will be transferred via secure electronic means for incorporation in the final data set. All individuals scanned at the McLean Hospital are checked in using their name, address and social security number.

3.4.2.3. Formal Reading of MRI Study: It is the policy of the McLean Hospital that all research subjects have a VA brain scanning sequence that is formally read by a person qualified to read MRI studies. This formal reading does have the subject name on it. The data that will be used for the study will only be marked with the subject ID.

3.4.2.4. RSA Data: Electroencephalogram (ECG) data will be collected 9 times during the study, three times at the McLean Hospital prior to each scan and before and after evaluations at weeks 4, 8, and 12 at the ENRMH. This data will be collected using a hand held device, a Bittum Faros, and transferred to a VA laptop computer where it will be processed and blinded before being sent through secure electronic means to [name], Co-Investigator for analysis. [name] will then send the analyzed data back for incorporation into the final database. The software that will be used to transfer the data from the Bittum Faros will be put on the VA computers by the VABHCS Information Technology (IT) staff.

3.4.2.5. Storage: Data will be stored in the REDCap database that will be created within the VA system, scan data will be stored in the locked McLean hard drives which are backed up regularly, the original ECG recordings will be stored on the VA network in a designated file. The ECG data sent to [name] will not contain HIPPA identifiers, when the data is returned it will be saved on a VA computer. The final data set will incorporate REDCap, imaging and RSA data. The management of the REDCap database and merging of the other databases into the final data will be done by the study statistician and Healthcare Specialist in accordance with VA regulations. The desktop computer will be stored in the Project Manager's Office, The laptops will be stored in [name] and the research staff's office and will be taken to the McLean Hospital as needed. [name] will also be Teleworking such that she will take her computer with her to her home and appointments, this computer will be encrypted. Papers with personal information will be kept in the offices of [name], the Project Manager and research staff in locked filing cabinets when not in use. Data regarding scan acquisition will be kept in a locked filing cabinet at the McLean Hospital or on secure servers. A Final Copy of the Database will be stored at the VABHCS on the VA network. One copy will be stored on the PI's VA laptop, a third copy will be provided to the study statistician. The database is owned by the VA.

3.4.2.6. Access and Use: Only members of the research team and individuals providing goods and services through contracts or Interagency Personnel Agreements (IPAs) will have access to the data. When study personnel are no longer members of the research team, they will no longer have access to the study data. The exception would be through the Data Management Access Plan

submitted with the Merit application.

3.4.2.7. Statistical Analysis: The data from REDCap, MRI/MRS and RSA will be merged into a final dataset for analysis by study statistician. The final dataset will be a Limited Data set in which the only HIPPA identifier will be the date of data collection. This data collection and analysis plan was included in the submitted proposal that was approved by the VACO, such that they were aware that data was going to be acquired and transferred outside of the VABHCS.

3.4.2.8. Security Measures: There are security measures in place at the VABHCS, the Data Coordinating Center, and the McLean Hospital.

3.4.3.1. Will VA data be combined with non-VA data: Not Applicable, all data is VA data, as data collected at the McLean Hospital is obtained under a contract. VACO has approved for [name] to be off-site at the McLean Hospital to oversee the imaging component of the study. [name] has appointments at the VABHCS, the McLean Hospital, and Boston University School of Medicine, the site of the Data Coordinating Center. VACO has approved [name] to have off-site time, such that she can use combined data while on VA time.

3.4.3.1. Identify any VA research activities occurring at non-VA sites: All imaging acquisition and analysis will take place at the McLean Hospital. [name] will conduct analysis of the ECGs for RSA off site with data that does not contain personal identifiers but will contain the data of acquisition. The study statistician will merge the data from REDCap, analyzed spectroscopic data, and RSA data into a final dataset.

3.4.3.2. Existing Protocols: Not Applicable

3.4.3.3. Provide a copy of any memorandum of understanding (MOU) with the non-VA entity describing data ownership or data security arrangements for the “collaborative” study: The McLean Contract provided for IRB approval and contains information regarding data ownership and data security. The contract for data management and data security that will contain Memorandum of Understanding (MOU) or contract describing the data ownership and security arrangements will be submitted to the IRB for approval before the data management and analysis can proceed.

3.4.3.4. This protocol does not collect non-VA research.

3.4.3.5. Uses and Disclosures of Protected Health Information (PHI): The data will only be used for research. The REDCap, ECG and MRI databases will only identify participants by their subject ID. Of the 18 HIPPA identifiers, only the date of date collection will be included in the Limited Final Database. The Final Database will include the dates of the assessment, which would not pose a reasonable risk of allowing the subject to be identified. There will be a separate database in REDCap with contact information, such that the PI or other research staff can contact subjects. The protections relating to HIPPA will be followed.

3.4.3.6. Researchers and Study Team Members: All research team members will be identified in the IRB approved study. Study team members are defined as non-VA employees who are involved in the contracts. Only researchers and study team members will have access to the data with the exception of the required regulators. While at the McLean Hospital, member of the McLean staff, who are not part of the research team, will interact with subjects at check in.

3.4.3.7. The Principal Investigator, [name] will have at the start of the study the following appointments: 1) a 3/5th appointment at the VABHCS VA; 2) an appointment at the Boston University School of Medicine for which she is compensated for work that is non-overlapping with this study; and 3) a without compensation appointment at the McLean Hospital.

(i) VA duties: The PI's 3/5th VA appointment includes clinical time as a member of the department of psychiatry at VABHCS and her duties as the PI of this study

(ii) VA duty locations: The VA duty locations are the VABHCS for clinical duties related to VABHCS and the conduct of this study.

(iii) VA tours of duty or time allocations: The PI's 3/5th VA appointment is equivalent to 24 hours a week plus a 30 minute meal break for period of work over 4 hours. This study will be run using the same structure that has worked for the civilian version of this study. In order to provide intervention times such that individual who are and are not employed can participate in the study, the interventions will be conducted from 8 am to 9:30 am and from 5 pm to 6:30 pm on Monday and Wednesday, the days of the intervention can be changed or additional sessions added as needed. The week 4, 8 and 12

evaluations that take place before and after the interventions and take around 45 minutes. To accommodate this schedule, [name] VA tour of duty will be from 7:30 am to 8:00 pm on Monday and Wednesday which includes a 30 minute meal break. After subtracting 30 minutes for lunch each day this results in two 12-hour tours, 24 hours or 3/5th time.

(iv) Issues related to data ownership: All data collected at the McLean Hospital will be collected under a contract which will state that the data belong to the VABHCS. All data analyzed by [name] belongs to the VABHCS. Research information protection and data security requirements. The protocol approved by Veterans Administration Central Office (VACO) included permission for [name] to be off site to oversee the collection and analysis of data at the McLean Hospital and for [name], [name], the study physicist to have access to a Limited Data Set. HIPPA identifiers will remain within the REDCap database, the VA Medical Health Record and the McLean Medical Health Record.

3.5. Analysis Plan

3.5.1. Data Management and Analysis Plan: The study statistician and Healthcare Specialist will be responsible under a contract for data management and statistical analysis for the project. The Healthcare team will convert the REDCap shell from an earlier study and provide the monitoring reports, create of the final database. The study statistician will oversee the statistical analysis with the help of the Healthcare Specialist. Descriptive statistics will be generated for baseline data and distributions between the yoga intervention and walking intervention will be compared using two-sample t-tests and chi-square or Fisher's exact tests to assess effectiveness of randomization. Descriptive statistics include means and standard deviations for continuous variables and group sizes and proportions for categorical variables. All analyses will be performed at the $\alpha = 0.05$ level of significance. Should groups have unequal distributions at baseline, relevant variables will be incorporated in subsequent linear models that will be used to examine intervention efficacy. In order to address the study aims of assessing the relative longitudinal change independent variables between yoga intervention and walking intervention groups over time, data will be collected at four time points, pre-randomization, and at weeks 4, 8, and 12. Mixed linear model analyses will be performed focusing on the group x time interaction for the primary effects to be statistically modeled. These analyses will allow for inclusion of data at differing numbers of time points per subject if needed. We will examine different within-subject correlation structures for our interaction model and determine the optimal structure by comparing Akaike information criteria (AIC) values. The correlation structure that yields the lowest AIC will be adopted. Subjects who change antidepressant medications during the study will be included in intent to treat analysis, but will be co-varied for medication changes. Potential cohort effects will be statistically addressed by controlling for group profiles, including group size, breakdown by sex of attendees, instructor, group parameters such as individual or group sessions, and group cohesion/overlap.

3.5.1. Data Management: The study statistician will provide leadership and expertise in data collection, management and analyses, encompassing database design, implementation of quality control procedures, technical support, and data sharing. A close interaction between data management staff and research team members will result in procedural consistency, efficiency of the study-wide systems, and ultimately produce the highest quality data. Data collection strategies will include web-based assessments using VA REDCap software. When possible, data will be collected on desktop computers, or laptops, negating the need for double entry. Electronic forms will include required fields, skip patterns, and validation resulting in more complete and "cleaner" data at capture. All participants will be assigned a unique identifier (ID) and personal identifiers that must be collected and used for consent and follow up will be stored in a separate database apart from study data. Analysed data from McLean Hospital and [name] will be provided via a VA approved system (e.g., AZURE)

3.5.1. Analysis of Hypotheses (Aim 1: Hypotheses 1. Aim 2: Hypotheses 2. Aim 3: Hypothesis 3)

Hypothesis 1. a. Depressive Symptoms: The yoga group will have decreased depressive symptoms compared to the walking group. There will be a significant within-group change (decrease) in

depressive symptoms over time, using a mixed linear model analogue of repeated measures analysis-of-variance with independent groups in MDD subjects assigned to the yoga group.

Hypothesis 1. b. Mood Scales: There will be a greater improvement in mood (as measured by the EIFI and STAI), and sleep (as measured by the PSQI) in the yoga group compared to the walking group.

Hypothesis 2. a. GABA: GABA levels will increase in the yoga group. There will be a within-group change in GABA levels over time using a mixed linear model analogue of repeated measures analysis-of-variance with independent groups in MDD subjects assigned to the yoga group.

Hypothesis 2. b. Group Differences: There will be a between-group difference in GABA levels over time using linear modeling comparing the yoga group with the walking group.

Hypothesis 3. a. RSA: There will be tonic increase in post intervention recovery RSA in the yoga but not the walking group.

Hypothesis 3. b.: There will be an increase (from baseline to end of week 12) in the difference between pre- and post-intervention in the rest and the recovery RSA in the yoga group.

Hypothesis 4. a. Exploratory Concurrent Antidepressants: The yoga group but not the walking group will have a decrease in depressive symptoms regardless of antidepressant treatment at the beginning of the study.

Hypothesis 4. b. Exploratory PTSD Symptoms: If PTSD symptoms are present at screening, there will be a greater decrease in PTSD symptoms in the yoga compared to the walking group as measured by CAPS and PCL-C.

Hypothesis 4. c. Resting State Connectivity will increase over the course of the study with greater increases in the yoga group.

Hypothesis 4. d. Executive Function will increase over the study as measured by the Stroop, Digit Symbol test and fMRI activation.

3.5.2. Power Analysis for Depressive symptoms and Mood Scales: Based on the power analyses below, in order to achieve adequate power for all analyses, n=70 subjects, n=35 in the yoga and n=35 in the walking intervention must complete the interventions. Using Study 4 data in subjects with MDD in the LDG, the repeated measures ANOVA for EIFI scores from screening to the completion of the intervention did not reach statistical significance in the group of n=15 (baseline: 3.1 ± 2.2 and week-12: 3.9 ± 2.7 , $F_{1,13} = 1.097$, $p = 0.31$), a post hoc power analysis was conducted, which determined that the achieved effect size was $f = .281$, with 52% power. Based on this same effect size, an a priori power calculation was conducted, which determined that **n=35** subjects would be needed to detect significant differences for BDI-II, STAI, and EIFI scores from screening to the completion of the intervention, with effect size $f = .281$, with $< = .02$ to account for multiple comparisons, and 81% power. As the power analysis for the EIFI requires the largest number of subjects (n=70), which will be used to determine sample size. In order for 70 subjects to complete the intervention, assuming a 20% drop out, 84 subjects will be randomized.

3.5.3. Power Analysis for GABA: Consistent with our analytic plan for the longitudinal questions at-hand, we can compute the statistical power for Hypothesis II an analysis sample of **n=26** subjects in each of the study groups using the mixed linear model analogue of repeated measures analysis-of-

variance with independent groups. We used nQuery Advisor, version 7.0 for these computations. Using GABA level as the dependent variable of interest and employing the observation from Study 2 in which the walking intervention showed no change in GABA over the 12-week intervention, it is predicted that GABA levels will not change over time in the walking group. We hypothesize that the yoga group will show mean GABA/Cr = 0.28, 0.285, and 0.32 at the three study time points and that the walking group will show mean GABA/Cr = 0.28, 0.28, and 0.28. Assuming a common standard deviation at each time point of 0.06 and a within-subject correlation of 0.65, we will have 80% power to detect the above noted pattern of repeated mean GABA/Cr with a two-sided alpha of 0.05. With the same data configuration, we will have 85% power should the within-subject correlation be as high as 0.70.

3.5.4. Tonic changes in Recovery RSA from screening to 12 weeks: The GEE of changes in recovery RSA in the full cohort (n=27) over 12 weeks was significant in Study 4; however, only the recovery RSA values in the smaller LDG (n=14) were used for the power analysis, as this reflects the dosage that will be utilized in the proposed study. While the repeated measures ANOVA did not reach statistical significance in the LDG (screening mean = 7.7 ± 2.5 and 12 week mean = 8.2 ± 2.9 , $F_{1,12} = 1.094$, $p = 0.315$), a post hoc power analysis was conducted, which determined that the achieved effect size was $f = 0.291$, with 52% power. Based on this same small to medium effect size, an a priori power calculation that includes two groups (yoga and walking) was conducted, which determined that **n=34** subjects would be necessary to detect significant differences in RSA at effect size $f = 0.291$, with 90% power.

3.5.5. Acute changes in RSA at 12 weeks (pre and post yoga intervention): Half way through Study 4, an RSA collection was added prior to the 12-week yoga intervention, which allowed acute changes in RSA to be calculated. An ANOVA of rest stage changes reached statistical significance; 12-week pre intervention resting mean = 4.9 ± 1.8 and 12-week post intervention resting mean = 5.7 ± 1.6 ($F_{1,14} = 11.056$, $p = .005$). A post hoc power analysis was conducted, which determined that the achieved effect size was $f = .858$, with 99% power. Based on this same large effect size, an a priori power calculation was conducted, which determined that **n=10** subjects would detect significant differences at effect size $f = .858$, with alpha = .01 and two groups (yoga and walking) would achieve 90% power. An ANOVA of rest stage changes reached statistical significance; 12 week pre intervention recovery mean = 6.7 ± 2.4 and 12 week post intervention recovery mean = 8.1 ± 3.4 ($F = 3.819$, $p = 0.070$). A post hoc power analysis was conducted, which determined that the achieved effect size was $f = 0.504$, with 96% power. Based on this same large effect size, an a priori power calculation was conducted, which determined that **n=20** subjects would detect significant differences at effect size $f = 0.504$, with $\alpha = .01$ and two groups (yoga and walking) would achieve 90% power.

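### Hypothesis 1a spells out only a within-yoga test of depressive symptoms, in conflict with the group x time interaction in the general plan, and nothing says which one decides

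*Protocol*

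**What the plan says.** Hypothesis I in protocol section 1.0 is comparative: more improvement with yoga than with walking. In protocol 3.5.1, Analysis of Hypotheses, Hypothesis 1a opens the same way: "The yoga group will have decreased depressive symptoms compared to the walking group". Its second sentence, the only one that describes a test, begins "There will be a significant within-group change (decrease) in" depressive symptoms over time. It ends by describing the model as a repeated-measures "analysis-of-variance with independent groups in MDD subjects assigned to the yoga group".

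The general paragraph (protocol 3.5.1, Data Management and Analysis Plan) names a different test: "Mixed linear model analyses will be performed focusing on the group x time interaction for the primary effects to be statistically modeled". SAP D.17 carries the same sentence. The SAP has no text for individual hypotheses.

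GABA is handled differently. Hypothesis 2a is a within-yoga statement worded much like 1a, and Hypothesis 2b then adds: "There will be a between-group difference in GABA levels over time using linear modeling comparing the yoga group with the walking group". Depression has no such second item, because Hypothesis 1b covers mood scales and sleep.

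**The concern.** The two places name tests of different questions. A within-yoga decrease asks whether scores fall over 12 weeks in people who do yoga. The group x time interaction asks whether they fall more than with walking, which is the trial's stated aim.

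The two tests can disagree in this trial, because a fall in both arms is to be expected. Section 3.2 justifies walking as an active control on the ground that exercise improves mood. Entry requires an HDRS of at least 14 at screening, which invites regression to the mean. The yoga arm's fall therefore mixes any specific yoga effect with natural recovery, regression to the mean, and the attention and exercise that walking also provides. If the second sentence of Hypothesis 1a were taken as the deciding rule, the primary hypothesis could be reported as supported without the randomized comparison contributing. With no stated precedence, that choice could be made after the data are seen.

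**Working it through.** **Inputs from the documents**
- Completers: 35 per arm (protocol 3.5.2).
- Significance level: 0.05 in the general plan, 0.02 in the Aim 1 power calculation. Two-sided testing is assumed.
- Visits: four (pre-randomization and weeks 4, 8 and 12).
- Pilot BDI-II change with two classes a week: a fall of 17.7, SD of change 9.3 (protocol 2.2.h), so 17.7/9.3 = 1.90 SD.

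**Not in the documents:** an SD or expected change for the HDRS, and any depression change under walking. BDI-II points below are therefore an assumption. The results in SD units need no scale.

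**1. Does the plan's own power figure show which test was meant?**
Repeated-measures formula: λ = f² × N × m / (1 − ρ), with m = 2 occasions and ρ = 0.5 (both assumed).
- f = 0.281, N = 35: λ = 0.0790 × 35 × 2 / 0.5 = 11.05. At alpha 0.02, power is 0.806 as a one-group within test and 0.805 as a two-group interaction with 35 subjects in total. Both agree with the stated 81%.
- N = 15, alpha 0.05: power 0.527, which agrees with the stated 52%.

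So the calculation reproduces but cannot settle the matter, since both tests give the same figure. The effect size itself comes from a one-arm pre-post change in the EIFI, not from a yoga-walking difference in the HDRS.

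**2. Within-yoga paired t-test when both arms fall equally**
Noncentrality = (common fall / SD of change) × √35, with 34 df. The table gives the chance of a significant decrease at two-sided 0.05.

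| Common fall (SD of change) | BDI-II points if SD = 9.3 | Chance |
|---|---|---|
| 0 | 0 | 2.5% |
| 0.22 | 2 | 24% |
| 0.34 | 3.2 | 50% |
| 0.49 | 4.5 | 80% |
| 0.86 | 8 | 99.9% |

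At alpha 0.02 the 50% and 80% points move to 0.41 SD (3.8 points) and 0.56 SD (5.2 points).

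**3. Within-yoga four-visit F test (3, 102 df)**
Assume a linear fall d, SD 9.3 at each visit and correlation 0.5. The SD of change is then 9.3 × √(2 × 0.5) = 9.3. The squared deviations of the four visit means sum to 5d²/9, so λ = 35 × (5d²/9) / (9.3² × 0.5).
- d = 17.7/4 = 4.4 points: λ = 8.80, chance 68%.
- d = 17.7/3 = 5.9 points: λ = 15.65, chance 92%.

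The one-quarter and one-third shares are illustrative. The paired t-test gives 78% and 95% at the same falls, so the result depends on which within-arm test is run.

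**4. Group x time test, same settings**
Simulated with equal falls in both arms from 0 to 17.7 points, the interaction is significant in 4.4% to 5.7% of trials, which is the nominal 5% within simulation error.

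**The case against.** The best defence is that the right test is already planned. The general paragraph and SAP D.17 both tie the group x time interaction to the study aims, and depression is Aim 1. This stands. A reader might infer that the plan has no between-group test for depression, and the documents do not support that.

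A reader might also infer that walking data play no part in the Hypothesis 1a test. That is not established. The model is described as having independent groups, and protocol 3.5.3 uses the same phrase for a calculation with both arms. A within-yoga contrast taken from a two-arm model is a fair reading. It would still be a within-yoga contrast, so it would not test yoga against walking.

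Nor is Hypothesis 1a, read in full, satisfied by a yoga-only fall, because its first sentence requires a comparison with walking. That is correct, but no test is attached to that sentence.

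Finally, it would be too strong to say that the within-yoga test succeeds in most trials when yoga has no advantage. That depends on a shared fall. If neither arm changes, a significant decrease appears 2.5% of the time, and at a common fall of 2 BDI-II points the paired test succeeds in 24% of trials.

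**Conclusion.** The concern holds as an unresolved conflict over which test decides the primary hypothesis. The only test spelled out within Hypothesis 1a cannot show that yoga beats walking. The general plan and the SAP name a test that can. Neither document gives one precedence over the other, and the between-group item supplied for GABA is missing for depression.

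If the within-yoga test were used, its false-success rate would be set by the size of the fall the two arms share. It passes 50% at about a third of an SD of change and 80% at about half an SD, both well below the 1.90 SD fall seen in the pilot. The point-scale figures borrow the pilot BDI-II SD, and the four-visit figures also assume a linear fall and a correlation of 0.5. The conclusion about which question each test answers rests on none of these assumptions.

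**What to change.** In protocol 3.5.1, replace the second sentence of Hypothesis 1a with: *This will be tested by the yoga-minus-walking difference in change in HDRS (group x time) in the mixed model using both randomized arms.* The SAP has no Hypothesis 1a sentence to edit, so add a line to D.17 stating that this interaction decides Hypothesis 1a. Report the within-yoga and within-walking changes side by side, each as a mean with a 95% confidence interval, and label them descriptive and not sufficient on their own to support Hypothesis I.

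The cost is one replaced sentence and one or two added lines. The data and the model are already planned. The downside is that success on the primary hypothesis becomes harder to reach than with a within-yoga test.
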